13.2. Assessing Adverse Events

In conjunction with the medical monitor, the Investigator will evaluate adverse events to ensure the events are categorized correctly. Elements of categorization will include:

- Seriousness/Classifications (see definition in section 13.1).
- Causality or Relatedness – i.e. the relationship between the test article, study treatment or study procedures and the adverse event (not related, unlikely related, possibly related, or related)
- Adverse Event Severity – Adverse event severity is used to assess the degree of intensity of the adverse event (mild, moderate, or severe)
- Outcome – not recovered or not resolved, recovering or resolving, recovered or resolved with sequelae, recovered or resolved, death related to adverse event, or unknown.
- Actions Taken – none, temporarily discontinued, permanently discontinued, or other.

Causality Assessment

Causality Assessment – A determination of the relationship between an adverse event and the test article, study treatment, or the study procedures. The test article, study treatment, or study procedures relationship for each adverse event should be determined by the investigator using these explanations:

- Not Related- An adverse event that is not related to the use of the test article, study treatment, or study procedures.
- Unlikely Related – An adverse event for which an alternative explanation is more likely, e.g. concomitant treatment, concomitant disease(s), or the relationship of time suggests that a causal relationship is not likely.
- Possibly Related – An adverse event that might be due to the use of the test article, or to the study treatment or study procedures. An alternative explanation, e.g. concomitant treatment, concomitant disease(s), is inconclusive. The relationship in time is reasonable. Therefore, the causal relationship cannot be excluded.
- Related – An adverse event that is listed as a possible adverse effect (device) or adverse reaction (drug) and cannot be reasonably explained by an alternative explanation, e.g. concomitant treatment of concomitant disease(s). The relationship in time is very suggestive, e.g. it is confirmed by de-challenge and re-challenge.

Severity Assessment

Severity Assessment – A qualitative assessment of the degree of intensity of an adverse event as determined by the Investigator or reported to him/her by the subject. The assessment of severity is made irrespective of test article, study treatment or study procedure relationship or seriousness of the event and should be evaluated according to the following scale:

- Mild – Event is noticeable to the subject but is easily tolerated and does not interfere with the subject's daily activities.
- Moderate – Event is bothersome, possible requiring additional therapy, and may interfere with the subject's daily activities.
- Severe – Event is intolerable, necessitates additional therapy or alteration of therapy and interferes with the subject's daily activities.

Clinical Study Protocol
Johnson & Johnson Vision Care, Inc.

13.3. Documentation and Follow-Up of Adverse Events

The recording and documenting of adverse events (ocular and non-ocular) begin when the subjects are exposed to the test article, study treatment or study procedure. Adverse events reported before the use of test article, start of study treatment, or study procedures will be recorded as medical history. However, if the condition deteriorates at any time during the study it will be recorded and reported as an AE. Untoward medical events reported after the subject's exit from the study will be recorded as adverse events at the discretion of the Investigator.

Upon finding an adverse event, the Principal Investigator will document the condition in the subject record and in the eCRFs and complete the Adverse Event eCRF.

Complete descriptions of all adverse events must be available in the subject record. All Adverse Events including local and systemic reactions not meeting the criteria for "serious adverse events" shall be captured on the appropriate case report form or electronic data system. All adverse events occurring while the subject is enrolled in the study must be documented appropriately regardless of relationship.

It is the Investigator's responsibility to maintain documentation of each reported adverse event. All adverse events will be followed in accordance with applicable licensing requirements. Such documentation will include the following:

- Adverse event (diagnosis not symptom).
- Drawings or photographs (where appropriate) that detail the finding (e.g., size, location, and depth, etc.).
- Date the clinical site was notified.
- Date and time of onset.
- Date and time of resolution.
- Adverse event classification, severity, and relationship to test articles, as applicable.
- Treatment regimen instituted (where appropriate), including concomitant medications prescribed, in accordance with applicable licensing requirements.
- Any referral to another health care provider if needed.
- Outcome, ocular damage (if any).
- Likely etiology.
- Best corrected visual acuity at the discovery of the event and upon conclusion of the event, if the AE is related to the visual system.

Upon discovery of an AE that is deemed 'possibly related' or 'related' to the test article or study procedures (whether related to the visual system or not), an AE review form [REDACTED] must be completed. Additional dated and initialed entries should be made at follow-up evaluations. Separate forms must be completed for each eye if the AE is bilateral.

In addition, if an infiltrate(s) is present, he/she will complete the Corneal Infiltrate Assessment eCRF. Where necessary, a culture of the corneal lesion will be collected to determine if the infection is microbial in nature. If cultures are collected, the date of culture collection and laboratory utilized will be recorded.

Changes in the severity of an AE shall be documented to allow an assessment of the duration of the event at each level of intensity to be performed. Adverse events characterized as intermittent require documentation of the onset and duration of each episode. Changes in the assessment of relationship to the Test Article shall also be clearly documented.

Subjects who present with an adverse event shall be followed by the Investigator, within licensure, until all signs and symptoms have returned to pre-treatment status, stabilized, or been satisfactorily resolved. If further treatment beyond licensure is required, the subject will be referred to the appropriate health care provider. The Investigator will use his/her clinical judgment as to whether a subject reporting with an adverse event will continue in the study. If a subject is discontinued from the study, it will be the responsibility of the Investigator to record the reason for discontinuation. The Investigator will also document the adverse event appropriately and complete the Adverse Event eCRF. Any subjects with ongoing adverse events related to the test article, study treatment or study procedures, as of the final study visit date, should be followed to resolution of the adverse event or until referral to an appropriate health care provider, as recommended by the Investigator. Non-ocular adverse events

Clinical Study Protocol
Johnson & Johnson Vision Care, Inc.

that are not related to the test article, study treatment, or study procedures may be recorded as "ongoing" without further follow-up.

13.4. Reporting Adverse Events

The Investigator will notify the Sponsor of an adverse event by EDC System, e-mail, or telephone as soon as possible and no later than 24 hours from discovery for any serious /significant adverse events, and 2 days from discovery for any non-significant adverse event. In addition, a written report will be submitted by the Principal Investigator to the IEC/IRB according to their requirements. The report will comment whether the adverse event was considered to be related to the test article, study treatment or study procedures.

Reporting Adverse Events to Sponsor

Serious/Significant Adverse Events

The Investigator will inform the sponsor of all serious/significant adverse events occurring during the study period as soon as possible by EDC System, e-mail or, telephone, but no later than 24 hours following discovery of the event. The Investigator is obligated to pursue and obtain information requested by the Sponsor in addition to that information reported on the eCRF. All subjects experiencing a serious/significant adverse event must be followed up and all outcomes must be reported.

When medically necessary, the Investigator may break the randomization code to determine the identity of the treatment that the subject received. The Sponsor and study monitor should be notified prior to unmasking the test articles.

In the event of a serious/significant adverse event, the Investigator must:

- Notify the Sponsor immediately.
- Obtain and maintain in the subject's records all pertinent medical information and medical judgment for colleagues who assisted in the treatment and follow-up of the subject.
- Provide the Sponsor with a complete case history which includes a statement as to whether the event was or was not related to the use of the test article.
- Notify the IEC/IRB as required by the IEC/IRB reporting procedure according to national regulations.

Unanticipated (Serious) Adverse Device Effect (UADE)

In the event of an Unanticipated (Serious) Adverse Device Effect (UADE), the Investigator will submit a report of the UADE to the Sponsor and IEC/IRB as soon as possible, but no later than 24 hours after the Investigator first learns of the effect. This report is in addition to the immediate notification mentioned above.

The Sponsor must conduct an evaluation of the UADE and must report the results of the evaluation to FDA, the IEC/IRB and participating Investigators within 10 working days after the Sponsor first receives notification of the effect.

Non-Serious Adverse Events

All non-serious adverse events, including non-serious adverse device effects, will be reported to the sponsor by the Investigator no later than 2 days from discovery.

Reporting Adverse Events to the Responsible IEC/IRB and Health Authorities

Adverse events that meet the IEC/IRB requirements for reporting must be reported within the IEC/IRB's written guidelines. Each clinical site will refer to and follow any guidelines set forth by their Approving IEC/IRB. Each clinical site will refer to and follow any guidelines set forth by their local governing Health Authorities.

The Sponsor will report applicable Adverse Events to the local health authorities according to the written guidelines, including reporting timelines.

Clinical Study Protocol
Johnson & Johnson Vision Care, Inc.

13.5. Event of Special Interest

None

13.6. Reporting of Pregnancy

Subjects reporting pregnancy (by self-report) during the study will be discontinued after the event is recorded as an Adverse Event. Once discontinued, pregnant subject and their fetuses will not be monitored for study related purposes. Pregnant subjects are not discontinued from contact lens or solution related studies for safety concerns, but due to general concerns relating to pregnancy and contact lens use. Specifically, pregnant women are discontinued due to fluctuations in refractive error and/or visual acuity that occur secondary to systemic hormonal changes, and not due to unforeseen health risks to the mother or fetus.

14. STATISTICAL METHODS

14.1. General Considerations

Statistical Analysis will be undertaken by the sponsor or under the authority of the sponsor. A general description of the statistical methods to be implemented in this clinical trial is outlined below.

Descriptive summary tables (descriptive statistics and/or frequency tables) will be provided for all demographic and baseline characteristics, efficacy variables and safety variables. For continuous endpoints, the descriptive statistics will include the number of subjects and/or eyes (as appropriate), mean, standard deviation (SD), median, and minimum and maximum. For binary or categorical endpoints, the frequency distribution with the number and percentage of subjects and/or eyes (as appropriate) in each category will be calculated. Graphic displays may also be used to summarize the data. Unscheduled visits will be summarized separately.

All data summaries and statistical analyses will be performed using the SAS software Version 9.4 or higher (SAS Institute, Cary, NC)⁵.

14.2. Sample Size Justification

This study was not designed or powered to test any statistical hypotheses with respect to distance (4m) visual acuity. As this will be the first study that will utilize the tracking software (Open Source Physics – OSP) a total of 5 subjects (10 eyes) to complete the study was based on clinical considerations and operational feasibility. A total of 5 subjects under a 2×2 crossover design provides sufficient data to evaluate the efficiency of this new software.

14.3. Analysis Populations

Intention-to-Treat (ITT) Population:

Intention-to-treat population will include all randomized subjects. Subjects will be analyzed as per planned randomized treatment.

Safety Population:

All subjects who are administered any study intervention. Subjects will be analyzed as per actual treatment received.

Per-Protocol Population:

All subjects who successfully complete all visits and do not substantially deviate from the protocol as determined by the trial cohort review committee prior to database hard lock. Justification for the exclusion of subjects with protocol deviations from the per-protocol population set will be documented in a memo to file.

14.4. Level of Statistical Significance

Not applicable. No hypothesis testing will be performed for any endpoints in this study.

Clinical Study Protocol
Johnson & Johnson Vision Care, Inc.

14.5. Statistical Analyses

Handling of Missing Data

All data summaries and statistical analysis will be conducted using the observed case data without multiple imputation. The count of missing data will be provided in each listing and table provided.

14.6. Efficacy Analyses

All efficacy endpoints will be summarized for both the ITT and per-protocol population using observed case data without multiple imputation.

Primary Efficacy Endpoint

1. Distance Visual Acuity

Distance (6m) monocular HLHC logMAR visual acuity at fitting will be summarized and presented only descriptively by lens type and timepoint (if applicable). Summary statistics are described in section 14.1

Secondary Efficacy Endpoint

Not applicable.

Other Efficacy Endpoints

1. **Lens orientation measured over time with an automated lens tracking system following intentional misalignment** Data resulting from the processing of the videos of each subject eye (for each lens), will be summarized by parameter (rotation error magnitude [range: 0 to 180] and rotation error direction [base temporal or nasal]). The video processed will be approximately 5 minutes per eye per lens. The tracking software will measure the parameters at 5-second intervals, totaling for a plan of 60 observations per eye per lens. Rotation error magnitude is a continuous data point while the rotation error direction is nominal categorical data. Signed rotation will be derived based on rotation error magnitude and direction and will be included as part of the external data file detailed in section 15. Parameter data (rotation error magnitude, signed rotation, and rotation direction) reported (or derived) from the automated tracking system will be summarized as per section 14.1.

2. **Lens orientation recorded with an automated lens tracking system following eye movements**

In addition to collecting rotation error magnitude and direction following intentional misalignment, rotation error magnitude and direction will be recorded in each of the 8 cardinal gaze directions before and after eye movement. The signed rotation will be derived in the same manner as described above. Summaries will be provided for each parameter (rotation error magnitude, signed rotation, and rotation direction), timepoint (before and after eye movement) and gaze separately. Additional summaries will be provided for the 8 gazes combined.

The 8 cardinal gazes are:

- Up and to the right
- Upward
- Up and to the left
- Right
- Left
- Down and to the right
- Downward
- Down and to the left

3. **Settling Time following intentional misalignment**

The time (in seconds) required for the lens to settle (defined as returning to within 5 degrees of initial settled position) after intentional misalignment will be presented descriptively and summarized separately for each study lens. Summary statistics are described in section 14.1.

Clinical Study Protocol
Johnson & Johnson Vision Care, Inc.

4. Toric Lens Orientation

The distribution (counts, percentages) of eyes for the toric Orientation (in degrees) at 1- and 3-minutes after lens insertion will be summarized at fitting and by lens type. Summary statistics are described in section 14.1.

5. Subjective Vision, Comfort and Handling Scores

Vision, comfort, and handling items will be summarized separately and presented only descriptively by lens type and timepoint (if applicable). Summary statistics are described in section 14.1.

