2.2. Endpoints

2.2.1. Efficacy Endpoints

Primary Efficacy Endpoint

1. Distance (6m) Visual Acuity

Clinical Study Protocol
Johnson & Johnson Vision Care, Inc.

The primary endpoint for this study will be distance visual acuity measured monocularly at 6 meters after lens fitting under high-luminance high contrast (HLHC) lighting conditions using the Eurolens computerized logMAR VA chart. The logMAR VA score is a continuous endpoint.

Other (Exploratory) Efficacy Endpoints

1. Lens orientation measured over time with an automated lens tracking system following intentional misalignment

Each study lens will be rotated in the temporal direction from its original position to its worst case orientation (90° from its settled position for the AO1DfA lens which has a bidirectional stabilization design, and 180° from its settled position for the DT1fA lens which has a unidirectional stabilization design), followed by video capture of the lens orientation over a 5-minute period. Lens orientation data (rotation error magnitude and direction relative to the 6 o'clock position, and rotation error magnitude and direction relative to original settled position) will be calculated at 5-second increments through the measurement period. Rotation error magnitude will be recorded in degrees (0 to 180), and rotation error direction will be recorded as base temporal or nasal. For the DT1fA lens type, recovery from 90° misalignment will also be determined from the timepoint that it reaches this position during the recovery from 180° of misalignment.

2. Lens orientation recorded with an automated lens tracking system following eye movements

Lens settled orientation (rotation error magnitude and direction relative to the 6 o'clock position) in primary gaze will be measured. Lens orientation will then be measured again after the subject has been asked to perform an eye movement in each of the eight cardinal directions of gaze. The difference in orientation (magnitude and direction) from before eye movement to after eye movement will be determined.

3. Settling Time following intentional misalignment

The time (in seconds) required for the study lenses to settle (defined as returning to within 5 degrees of initial settled position) after intentional misalignment will be recorded for each eye and lens during the assessment of the lens orientation recorded with an automated lens tracking system (Other efficacy endpoint 1). Settling time is a continuous endpoint.

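### Signed rotation is summarised with linear mean, SD and median, although its scale breaks at ±180°, where the Control lens is deliberately started

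*Combined protocol and SAP*

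**What the plan says.** Section 2.2.1, Other Efficacy Endpoint 1, describes the manoeuvre: "Each study lens will be rotated in the temporal direction from its original position to its worst case orientation". For the Test lens this is "90° from its settled position for the AO1DfA lens which has a bidirectional stabilization design", and for the Control lens "180° from its settled position for the DT1fA lens which has a unidirectional stabilization design". On the scale it says: "Rotation error magnitude will be recorded in degrees (0 to 180), and rotation error direction will be recorded as base temporal or nasal". Sections 2.2.1 and 15.1 ask for the error against two references, 6 o'clock and the initial settled position.

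Section 14.6 then says: "Signed rotation will be derived based on rotation error magnitude and direction". Magnitude, signed rotation and direction "reported (or derived) from the automated tracking system will be summarized as per section 14.1". For continuous endpoints section 14.1 lists "mean, standard deviation (SD), median, and minimum and maximum".

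The readable text gives no circular statistic, no rule for a lens at or crossing 180°, and no step that follows the angle continuously along the recovery path. For this endpoint, section 14.6 does not say whether the summaries are made by time point.

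**The concern.** A signed angle running from −180° to +180° is continuous at 0° but not at its ends. Readings of +179° and −179° are 2° apart on the eye and 358° apart in the data file. Linear statistics work while all readings stay away from that break, but the protocol places the Control lens on it by design.

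Always turning the lens temporally does not prevent this. Against 6 o'clock, a small temporal settled offset carries the lens past 180° and its label becomes nasal. Against the settled position, any overshoot, or recovery through the nasal side, does the same.

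At stake are the signed mean, SD and median and the temporal/nasal percentages for the Control lens early in recovery. No hypotheses are tested (section 2.3), so descriptive summaries of this kind are the study's output on rotation.

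**Working it through.** **Inputs.** Control lens start 180° and Test lens start 90° from settled, turned temporally; magnitude 0 to 180 with a binary direction (section 2.2.1). Linear statistics (sections 14.1 and 14.6). Five completers, 10 eyes (section 14.2). Readings every 5 seconds over about 5 minutes (section 14.6).

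**The plan's own figure.** 300 s / 5 s = 60 readings per eye per lens, as section 14.6 states (61 if time zero is also counted). 5 subjects × 2 eyes = 10 eyes.

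**Step 1: the sign.** Let S = +M if temporal and −M if nasal, where M is magnitude. Against 6 o'clock, position after an exact 180° temporal turn = settled offset + 180°.

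- Settled 5° temporal: 5 + 180 = 185; 185 − 360 = −175, recorded as 175° nasal.
- Settled 5° nasal: −5 + 180 = +175, recorded as 175° temporal.

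These lenses are 10° apart on the eye and 350° apart on the signed scale.

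**Step 2: ten eyes, each 175° off, split five and five.**

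- Linear mean = (5 × 175 − 5 × 175)/10 = 0°.
- Median = (175 − 175)/2 = 0°.
- SD = √(10 × 175²/9) = 184.5°.
- Mean magnitude = 175°.
- Circular mean = atan2(mean sine, mean cosine) = atan2(0, −0.996) = 180°, with resultant length R = 0.996.
- Circular SD = √(−2 ln 0.9962) = 0.087 rad, about 5°.

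**Step 3: other splits.** With k of 10 eyes labelled nasal, linear mean = 175 × (10 − 2k)/10.

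| k nasal | Linear signed mean | Mean magnitude | Circular mean |
|---|---|---|---|
| 0 | 175° | 175° | 175° |
| 1 | 140° | 175° | 176° |
| 2 | 105° | 175° | 177° |
| 3 | 70° | 175° | 178° |
| 4 | 35° | 175° | 179° |
| 5 | 0° | 175° | 180° |

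For k = 6 to 10 the linear mean mirrors this down to −175°. The circular mean stays within 5° of 180° throughout.

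**Step 4: how often.** The documents give no distribution of settled offsets, so these are assumptions: normal offsets relative to 6 o'clock, independent eyes, an exact 180° turn, 20,000 simulated sets of 10 eyes.

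| Offset mean, SD | Sets with absolute signed mean < 90° | Median absolute signed mean |
|---|---|---|
| 0°, 3–10° | about 89% | 35–36° |
| 5°, 10° | 64% | 67° |
| 5°, 5° | 20% | 136° |
| 10°, 3° | about 0% | 170° |

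Mean magnitude is about 170° to 178° in all these cases. As a check on the first row, if each side is equally likely, P(4 to 6 nasal) = (210 + 252 + 210)/1024 = 0.656, and in Step 3 such a split gives an absolute mean of at most 35°. P(all on one side) = 2/1024 = 0.002.

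**The case against.** **Other planned outputs would expose the artefact.** A mean of 0° beside an SD of 184.5° and a mean magnitude of 175° would not be taken for good alignment. This stands and limits the harm, but it does not make the signed mean, SD or median correct.

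**The frequency is unknown.** A reader might infer that the Control lens's signed mean will usually sit near 0°. The documents do not support that. Relative to the settled position, a slight under-rotation, or some return before capture, keeps every label temporal and the mean is right. A consistent settled offset does much the same relative to 6 o'clock. Two eyes of one subject are also not independent, as Step 4 assumes.

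**The lens comparison.** A reader might infer that the comparison of lenses over time is distorted as a whole. Section 2.2.1 also has the Control lens's recovery determined from the moment it reaches 90°, which is away from the break, and magnitude is summarised separately. A reader might equally infer that the Test lens is immune because it starts at 90°. That is not established: it is bidirectional and Table 1 gives it marks at both 6 and 12 o'clock. If one mark is followed, a lens that recovers the other way settles near 180°. If the nearer mark is read, 90° is itself a boundary.

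**A convention may exist in redacted text.** This cannot be excluded. However, a rule that only assigns a sign at 180° would not repair a linear average across the break.

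**The endpoint is exploratory, in a five-completer feasibility study.** This is true and bears on priority.

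**Conclusion.** The rule is wrong as written, and the point is minor. Linear mean, SD and median are not valid summaries of signed rotation when readings lie on both sides of 180°, and the protocol starts the Control lens there. The signed mean can then be anywhere between −175° and +175° when every eye is 175° off.

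That this can happen follows from the documents' own scale, start position and statistics. Its frequency, from about 89% to about 0% of sets with an absolute mean below 90°, rests entirely on assumed offsets.

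The effect is confined to readings near 180°, mainly early in Control-lens recovery. Its share of the 60 readings is unknown because no recovery speed is given; if readings are pooled over time, the early ones still enter the pooled figure. Settling time and the primary endpoint, visual acuity, are untouched, and the documents do not support a claim that the study's lens comparison fails.

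**What to change.** In section 14.6, Other Efficacy Endpoint 1:

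- Summarise signed rotation by time point with circular mean and circular SD in place of linear mean, SD and median.
- Name rotation error magnitude as the main time-course summary. It is already planned and has no break at 180°. It is also needed where eyes recover by opposite sides: five eyes at +90° and five at −90° give R = 0, and the circular mean is then undefined.
- State that temporal/nasal percentages are not interpretable for readings close to 180°, with a pre-specified cut-off.
- If unwrapped angles are used, restrict them to individual eye paths and do not average them across eyes. A lens that recovers through the nasal side ends near 360° when fully settled, while one that returns the way it came ends near 0°. Five of each average (5 × 360)/10 = 180°, which moves the artefact to the end of recovery.
- State which mark is followed on the Test lens, since these circular summaries treat the angle on a 360° scale.

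The cost is a little more programming and a few sentences in section 14.6. Magnitude and direction are already in the external data file, so no new data are needed.
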